9.3 Other Response Parameters

Response should be maintained for 8 weeks.

CONFIDENTIAL

This document is confidential. Do not disclose or use except as authorized.

10 ADVERSE EVENT REPORTING REQUIREMENTS

All adverse events that occur after the initial dose of study treatment, during treatment, or within 30 days of the last study intervention need to be captured. Adverse events will be followed for 30 days after the last study intervention if a participant discontinues protocol treatment early. All AEs need to be followed until resolution.

10.1 Adverse Event (AE) Characteristics, Collection and Routine Reporting

An adverse event (AE) is any undesirable sign, symptom or medical condition or experience that develops or worsens in severity after starting the first dose of study treatment or any procedure specified in the protocol, even if the event is not considered to be related to the study.

All AEs (**grades 1-5**) whether reported by the participant, discovered during questioning, directly observed, or detected by physical examination, laboratory test or other means, will be recorded in the participant's medical record and on the appropriate study-specific case report forms.

- **NOTE:** Abnormal laboratory values or diagnostic test results constitute adverse events only if they are clinically significant (i.e. cause a cycle to be delayed, induce clinical signs or symptoms or require treatment or further diagnostic tests).

CTCAE term (AE description) and grade: The descriptions and grading scales found in the revised NCI Common Terminology Criteria for Adverse Events (CTCAE) version 4.0 will be utilized for AE reporting. All appropriate treatment areas should have access to a copy of the CTCAE version 4.0. A copy of the CTCAE version 4.0 can be downloaded from the CTEP web site http://ctep.cancer.gov/protocolDevelopment/electronic_applications/ctc.htm.

Attribution is the relationship between an adverse event and the study treatment. Attribution will be assigned as follows:

- Definite – The AE is clearly related to the study treatment.
- Probable – The AE is likely related to the study treatment.
- Possible – The AE may be related to the study treatment.
- Unlikely - The AE is doubtfully related to the study treatment.
- Unrelated - The AE is clearly NOT related to the study treatment.

Adverse events can be '**Expected**' or '**Unexpected**.'

- **Expected adverse events** are those that have been previously identified as resulting from administration of the agent. For the purposes of this study, an adverse event is considered expected when it appears in the current adverse event list (see Section 6.1), the Investigator's Brochure, the package insert or is included in the informed consent document as a potential risk.
- **Unexpected adverse events** are an adverse reaction, the nature or severity of which is not consistent with the applicable product information (e.g., Investigator's Brochure for an unapproved investigational medicinal product or package insert/summary of product characteristics for an

CONFIDENTIAL

This document is confidential. Do not disclose or use except as authorized.

approved product). An expected ADR with a fatal outcome should be considered unexpected unless the local/regional product labeling specifically states that the Adverse Drug Reaction (ADR) might be associated with a fatal outcome.

Reportable Adverse Events **must** be reported in routine study data submissions to the Overall PI on the adverse events case report forms (i.e. in InForm).

10.2 Serious Adverse Events (SAE) and Expedited Reporting

A serious adverse event (SAE) is any adverse event, occurring at any dose and regardless of causality that:

- Results in death (Grade 5)
- Is life-threatening. Life-threatening means that the person was at immediate risk of death from the reaction as it occurred, i.e., it does not include a reaction which hypothetically might have caused death had it occurred in a more severe form.
- Requires intensive inpatient medical interventions, including mechanical ventilation, pressor support, and/or fluid resuscitation, or emergent surgical operations. Unplanned hospital admission for febrile neutropenia, bacteremia or other documented infections, seizure, pancreatitis, thrombosis, nausea/vomiting, diarrhea, and other expected toxicities from the study treatment will not be considered a serious adverse event unless the severity of the condition is considered life-threatening and/or lead to intensive medical interventions or surgical procedure.
- Hospitalization admissions and/or surgical operations scheduled to occur during the study period, but planned prior to study entry are not considered SAEs if the illness or disease existed before the person was enrolled in the trial, provided that it did not deteriorate in an unexpected manner during the trial (e.g., surgery performed earlier than planned).
- Results in persistent or significant disability/incapacity. Disability is defined as a substantial disruption of a person's ability to conduct normal life functions.
- Is a congenital anomaly or birth defect; or
- Is an important medical event when, based upon appropriate medical judgment, it may jeopardize the participant and require medical or surgical intervention to prevent one of the outcomes listed above. Examples of such medical events include allergic bronchospasm requiring intensive treatment in an emergency room or at home; blood dyscrasias or convulsions that do not result in inpatient hospitalization, or the development of drug dependency or drug abuse.
- Per DFCI's Expedited Reporting requirements, the following events also require expedited (SAE) reporting:
 - Unexpected Grade 2 (moderate) and Grade 3 (severe) events that are possibly, probably or definitely related/associated with the intervention.
 - Unexpected Grade 4 (life-threatening or disabling) events regardless of attribution.
 - All Grade 5 (fatal) Events – When the participant is enrolled and actively participating in the trial OR when the event occurs within 30 days of the last study intervention.
 - Note: If the participant is in long term follow up, report the death at the time of continuing review.

CONFIDENTIAL

This document is confidential. Do not disclose or use except as authorized.

Events not considered to be serious adverse events are hospitalizations for:

- Routine treatment or monitoring of the studied indication, not associated with any deterioration in condition, or for elective procedures
- Elective or pre-planned treatment for a pre-existing condition that did not worsen
- Emergency outpatient treatment for an event not fulfilling the serious criteria outlined above and not resulting in inpatient admission
- Respite care

The Overall Principal Investigator/Sponsor ([name]) and the study team at the lead institution should be informed within **1 business day**, by email or phone of all SAEs that occur after the initial dose of study treatment, during treatment, or within 30 days after the last study intervention. In the event that the participating investigator does not become aware of the SAE immediately (e.g., participant sought treatment elsewhere), the participating investigator is to report the event **within 24 business hours after learning of it** and document the time of his or her first awareness of the event. Report serious adverse events by telephone, email or facsimile:

[name]
Pediatric Oncology
Dana-Farber Cancer Institute
[name]
Boston, MA 02215
[contact]
Email: [contact]
[contact]

At the same time, an e-mail should also be sent to the Lead Site clinical research coordinator listed on page one of this protocol.

Within the following 24-48 business hours, the participating investigator should relay follow-up information to the PI and study team as necessary.

10.3 AESI: An adverse event of special interest:

AESI is an adverse event (serious or non-serious) of scientific and medical concern specific to the Sponsor's product or program, for which ongoing monitoring and rapid communication by the Investigator to the Sponsor may be appropriate. Such events may require further investigation in order to characterize and understand them. AESIs may be added or removed during a study by protocol amendment.

10.4 New safety finding:

Any (other than reportable individual case safety report (ICSR)) safety issue that may require expedited reporting because providing information that may lead to a change in the known risk-benefit balance for the product and as mentioned, but not limited to, in the following regulatory texts: Europe: Volume 9A of the Rules Governing Medicinal products in the European Union (September 2008) Section 4.1; and US: FDA: 21 CFR Parts 312 Investigational New Drug Application- Section 312.32, (c) (1) IND safety reports.

CONFIDENTIAL

This document is confidential. Do not disclose or use except as authorized.

10.5 Reporting to the Institutional Review Board (IRB)

Investigative sites within DF/HCC will report all serious adverse events directly to the DFCI Office for Human Research Studies (OHRS).

Each investigative site will be responsible to report SAEs that occur at that institution to their respective IRB per their local IRB's policies and procedures in reporting adverse events. These sites will also complete a DF/HCC AE Reporting form and submit to the Overall PI and DFCI study team. The Overall PI and DFCI study team will then submit the DF/HCC AE Reporting form from outside institutions to the DFCI OHRS according to DFCI IRB policies and procedures in reporting adverse events.

10.6 Reporting to Regulatory Agencies

For multi-site trials where a DF/HCC investigator is serving as the principal investigator, each participating investigator is required to abide by the reporting requirements set by the DF/HCC. The study must be conducted in compliance with FDA regulations, local safety reporting requirements, and reporting requirements of the principal investigator.

The Overall PI, as study sponsor, will be responsible for all communications with the FDA and Health Canada. The Overall PI will report to the FDA and Health Canada, regardless of the site of occurrence, any serious adverse event that meets the FDA and Health Canada's criteria for expedited reporting following the reporting requirements and timelines set by the FDA and Health Canada.

10.7 Reporting to Hospital Risk Management

Participating investigators will report to their local Risk Management office any subject safety reports or sentinel events that require reporting according to institutional policy.

10.8 Pharmacovigilance Specifications and reporting to Sanofi

The sponsor-investigator [name]. of the Investigator-Sponsored Trial/Study (IST/ISS) will report the following information in English to the Sanofi Global Pharmacovigilance contact, **E-mail:** [contact] or **[contact] or **[contact]

1. Routine transmission of all Serious Adverse Events (SAEs) including pregnancy, overdose and Adverse Events of Special Interest (AESI), if any. These events must be transmitted within 1 business day of the ISS sponsor's awareness or identification of the event, *for Pre-marketing IST and post-marketing ISS with recently approved products.*
2. Routine transmission of SAEs related to the use of the Sanofi product must be transmitted within 1 business day of the ISS sponsor's awareness or identification of the event *for all other approved products.*
3. The reference safety information to be used by the ISS sponsor for evaluation of expectedness of adverse events shall be the current approved product label available in the country *(for an approved indication)/ the Investigator Brochure.*

CONFIDENTIAL

This document is confidential. Do not disclose or use except as authorized.

4. Any Periodic reports (e.g. Development Safety Update Report (DSUR)), submitted to Regulatory Authority must be transmitted to Sanofi at the time of submission.
5. *New Safety Findings* in a study pertaining to safety of product must be transmitted within 1 business day. (e.g., Data Safety Monitoring Board recommendations)
6. The study reports of any ISS must contain a section describing safety review and conclusion and must be reviewed by Sanofi before finalization.

11 DATA AND SAFETY MONITORING

11.1 Data Reporting

11.1.1 Method

The ODQ will collect, manage, and perform quality checks on the data for this study.

11.1.2 Data Submission

Sites are responsible for submitting data and/or data forms to the ODQ according to the schedule set by the ODQ.

11.2 Safety Meetings

The DF/HCC Data and Safety Monitoring Committee (DSMC) will review and monitor toxicity and accrual data from this trial. The committee is composed of clinical specialists with experience in oncology and who have no direct relationship with the study. Information that raises any questions about participant safety will be addressed with the Principal Investigator and the Lead Site study team.

The DSMC will meet quarterly and/or as often as necessary, as determined by the DSMC, if required to review toxicity and accrual data. Information to be provided to the committee may include: up-to-date participant accrual; current dose level information; DLT information; all grade 2 or higher unexpected adverse events that have been reported; summary of all deaths occurring within 30 days for Phase I or II protocols; for gene transfer protocols, summary of all deaths while being treated and during active follow-up; any response information; audit results, and a summary provided by the study team. Other information (e.g. scans, laboratory values) will be provided upon request.

11.3 Monitoring

Involvement in this study as a participating investigator implies acceptance of potential audits or inspections, including source data verification, by representatives designated by the DF/HCC Overall Principal Investigator (or Protocol Chair) or DF/HCC. The purpose of these audits or inspections is to examine study-related activities and documents to determine whether these activities were conducted and data were recorded, analyzed, and accurately reported in accordance with the protocol, institutional policy, Good Clinical Practice (GCP), and any applicable regulatory requirements.

All data will be monitored for timeliness of submission, completeness, and adherence to protocol requirements. Monitoring will begin at the time of participant registration and will continue during

CONFIDENTIAL

This document is confidential. Do not disclose or use except as authorized.

protocol performance and completion.

Please refer to section 17 Appendix II for more details.

12 REGULATORY CONSIDERATIONS

12.1 Protocol Review and Amendments

This protocol, the proposed informed consent and all forms of participant information related to the study (e.g., advertisements used to recruit participants) and any other necessary documents must be submitted, reviewed and approved by a properly constituted IRB governing each study location.

Any changes made to the protocol must be submitted as amendments and must be approved by the IRB prior to implementation. Any changes in study conduct must be reported to the IRB. The DF/HCC Overall Principal Investigator (or Protocol Chair) or his designee will disseminate protocol amendment information to all participating investigators.

All decisions of the IRB concerning the conduct of the study must be made in writing.

12.2 Informed Consent

All participants must be provided a consent form describing this study and providing sufficient information for participants to make an informed decision about their participation in this study. The formal consent of a participant, using the IRB approved consent form, must be obtained before the participant is involved in any study-related procedure. The consent form must be signed and dated by the participant or the participant's legally authorized representative, and by the person obtaining the consent. The participant must be given a copy of the signed and dated consent document. The original signed copy of the consent document must be retained in the medical record or research file.

12.3 Ethics

This study is to be conducted according to the following considerations, which represent good and sound research practice:

- US Code of Federal Regulations (CFR) governing clinical study conduct and ethical principles that have their origin in the Declaration of Helsinki
 - Title 21 Part 50 – Protection of Human Subjects
www.access.gpo.gov/nara/cfr/waisidx_02/21cfr50_02.html
 - Title 21 Part 54 – Financial Disclosure by Clinical Investigators
www.access.gpo.gov/nara/cfr/waisidx_02/21cfr54_02.html
 - Title 21 Part 56 – Institutional Review Boards
www.access.gpo.gov/nara/cfr/waisidx_02/21cfr56_02.html

CONFIDENTIAL

This document is confidential. Do not disclose or use except as authorized.

- Title 21 Part 312 – Investigational New Drug Application
www.access.gpo.gov/nara/cfr/waisidx_02/21cfr312_02.html
- State laws
- DF/HCC research policies and procedures
<http://www.dfhcc.harvard.edu/clinical-research-support/clinical-research-unit-cru/policies-and-procedures/>

It is understood that deviations from the protocol should be avoided, except when necessary to eliminate an immediate hazard to a research participant. In such case, the deviation must be reported to the IRB according to the local reporting policy.

12.4 Study Documentation

The investigator must prepare and maintain adequate and accurate case histories designed to record all observations and other data pertinent to the study for each research participant. This information enables the study to be fully documented and the study data to be subsequently verified.

Original source documents supporting entries in the case report forms include but are not limited to hospital records, clinical charts, laboratory and pharmacy records, recorded data from automated instruments, microfiches, photographic negatives, microfilm or magnetic media, and/or x-rays.

12.5 Records Retention

All study-related documents must be retained for the maximum period required by applicable federal regulations and guidelines or institutional policies.

12.6 Multi-Center Guidelines

This protocol will adhere to the policies and requirements of the Dana-Farber/Harvard Cancer Center. The specific responsibilities of the DF/HCC Overall Principal Investigator (or Protocol Chair), Coordinating Center, and Participating Institutions are presented in the Dana-Farber/Harvard Cancer Center Multi-Center Data and Safety Monitoring Plan (see Appendix II).

- The DF/HCC Overall Principal Investigator/Coordinating Center is responsible for distributing all IND Action Letters or Safety Reports to all participating institutions for submission to their individual IRBs for action as required.
- Mechanisms will be in place to ensure quality assurance, protocol compliance, and adverse event reporting at each site.
- Except in very unusual circumstances, each participating institution will order the agent(s) directly from the supplier. A participating site may order the agent(s) only after the initial IRB approval for the site has been forwarded to the Coordinating Center.

CONFIDENTIAL

This document is confidential. Do not disclose or use except as authorized.

13 STATISTICAL CONSIDERATIONS

13.1 Overview

This is a prospective study of clofarabine treatment for Histiocytosis patients. All patients will receive the same treatment with the standard dose of clofarabine (25 mg/m²/d). A single-arm design test will be used to estimate the response rate in Stratum 1. In addition, in an exploratory fashion, we will estimate the rates of response and toxicity in patients with LCH-related disorders (Stratum 2). Stratum 2 is a heterogeneous group of patients, and we wish to gather data in order to generate hypotheses about the response rates of the subgroups of Stratum 2 which could be tested in a future protocol.

13.2 Sample Size/Accrual Rate

Twenty evaluable participants in Stratum 1 will be required in order to have sufficient power to address the study's primary objective. To account for participants who enroll and are subsequently determined to be ineligible or unevaluable, a total of up to 25 participants may be enrolled in order to obtain 20 evaluable patients. At an estimated accrual rate of 10 participants per year, the accrual goal of 20 evaluable participants can be achieved in less than 4 years. It is estimated that up to 10 patients per year meeting the eligibility criteria for Stratum 2 are seen across all study sites (personal communication from [name]). Therefore, the estimated accrual rate of Stratum 2 patients is up to 5 patients per year, which allows for up to 20 patients in Stratum 2, though realistically, fewer of these rare patients are anticipated to be enrolled. We estimate a total study accrual of up to 45 patients (25 in Stratum 1, and 20 in Stratum 2).

Once the accrual goal of eligible patients for a given stratum is reached (with a 5-patient overage to account for potentially ineligible patients), that stratum will be closed to accrual. Once the accrual goal of evaluable patients is met within Stratum 1, the overall study will be closed even if fewer than 20 patients have been enrolled in Stratum 2. In the unlikely event that 20 patients are enrolled on Stratum 2 before Stratum 1 has met its accrual goal, Stratum 2 will be closed to accrual.

13.3 Study Design/Endpoints

The primary endpoint within each stratum will be the proportion of responders. A responder is defined as an eligible, evaluable participant who achieves either complete resolution or regression of disease, i.e., their disease gets "Better" per section 9.1, as the best overall response at any time up to and including the End of Cycle 2 assessment, which must be completed on Day 28 of Cycle 2 +/- 7 days, and must be completed prior to starting Cycle 3.

Secondary endpoints are:

- a) Progression-free survival (PFS), where time to event for PFS is the time from study enrollment until the time of first occurrence of new lesions, progressive disease, or death from any cause, or until last contact if no event occurs;
- b) Overall survival (OS), calculated as the time from enrollment until death or last contact;

CONFIDENTIAL

This document is confidential. Do not disclose or use except as authorized.

- c) Feasibility, which is assessed by the proportion of patients who experience a toxicity-event. Participants who have clofarabine stopped because of toxicity concerns will be considered to have experienced a toxicity-event. Otherwise, participants who complete therapy or who are removed from protocol therapy for reasons related to disease progression, second malignancy or death unrelated to protocol therapy will be considered to have successfully tolerated treatment; and,
- d) The proportion of participants reporting grades 3-4 toxicity, for each CTCAE v4.0 toxicity code.

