5 TREATMENT PLAN

Each patient can receive a maximum of 6 cycles of study treatment. Each treatment cycle will last 4 weeks (28 days) and a delay up to day 42 is allowed if necessary to meet eligibility criteria for starting subsequent cycles. Patients will be stratified into two groups for response analysis purposes:

Table 1: Treatment Plan for all Patients

INDUCTION			MAINTENANCE			
Cycle						
1	2		3	4	5	6
Clofarabine 25 mg/m ² /day Days 1-5 I.V. 2 hrs +/- 30 min		Disease Evaluation	Clofarabine 25 mg/m ² /day Days 1-5 I.V. 2 hrs +/- 30 min			

Induction: Clofarabine on Days 1-5 of each cycle, administered as I.V. infusion at 25 mg/m²/day. No drug treatment from Day 6 to Day 28. This cycle will be repeated once.

Evaluation of disease response (see Section 9) will be performed after 2 cycles of Induction Therapy. In the absence of disease progression, participants will be eligible to receive up to 4 cycles of Maintenance Therapy, which is identical to the Induction Therapy.

Maintenance: Clofarabine on Days 1-5 of each cycle, administered as I.V. infusion at 25 mg/m²/day. No drug treatment from Day 6 to Day 28. Cycle will be repeated for up to three more times every 28 days.

CONFIDENTIAL

This document is confidential. Do not disclose or use except as authorized.

Treatment may be administered on an outpatient basis. Expected toxicities and potential risks as well as dose modifications for clofarabine is described in Section 6. No investigational or commercial agents or therapies other than those described below may be administered with the intent to treat the participant's malignancy.

5.1 Criteria to Proceed with Cycle 1

The following assessment must be completed within 3 days prior to starting Cycle 1. **Patients need to re-meet lab eligibility criteria as described in section 3.1.**

1. Complete physical examination including height, weight and BSA.
2. Performance status $\geq 70\%$ (use Lansky score for age < 16 and Karnofsky score for age ≥ 16 , see Appendix I).
3. Concurrent medical conditions.
4. Hematology: CBC with differential and platelet count and peripheral blood smear.
5. Serum chemistries: Electrolytes (calcium, magnesium, phosphorus, sodium, potassium, chloride, and bicarbonate), blood urea nitrogen (BUN), creatinine, and serum glucose. Liver function tests (total protein/albumin, aspartate aminotransferase (AST), alanine aminotransferase (ALT), alkaline phosphatase (ALP), total bilirubin).
6. Uric Acid as clinically indicated.

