⁶ End of treatment disease assessment imaging window +/- 14 days from day 28 of Cycle 6.

⁷ All Follow-Up Assessments to be performed 12, 24, and 36 months from the off-treatment date (i.e. Day 28 of last administered cycle) +/- 31 days.

⁸ 12, 24, and 36 months after completion of therapy (i.e. Day 28 of last administered cycle)

CONFIDENTIAL

This document is confidential. Do not disclose or use except as authorized.

9 CRITERIA FOR RESPONSE – STRATUM 1

In contrast to leukemia or other malignancies the terms “remission” or “relapse” should be avoided. In accordance with the nature of Histiocytosis the following definitions should be applied to judge the effect of treatment. The response criteria stated below has been designed by the Histiocyte Society to be applied in therapeutic studies of LCH and should be used for therapeutic decisions.⁶⁸

Table 3: Definition of Disease State

Main Category	Sub-categories	Definition
Non-active Disease (NAD)		Resolution of all signs/symptoms (no evidence of disease)
Active Disease (AD)	Regressive Disease (Better)	Regression of signs/symptoms, and no new lesions.
	Stable Disease (Stable)	Persistence of signs or symptoms, and no new lesions.
	Progressive Disease* (Worse)	Progression of signs/symptoms and/or appearance of new lesions.

* Progression of skeletal lesions is defined as unequivocal enlargement of the size of existing lesions and/or appearance of new lesions.

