9.1 Definition of Response Criteria

Table 4: Three Categories of Response

Response Category	Definition
Better	
 Complete disease resolution (NAD) Regression (AD better)
Intermediate	
 Stable (unchanged)
Worse	
 Progression*

* Progression of skeletal lesions is defined as unequivocal enlargement of the size of existing lesions and/or appearance of new lesions. In patients with risk organ involvement the overall response (and hence therapeutic decision) depends on response in risk organs.

9.2 CRITERIA FOR RESPONSE – STRATUM 2

For PET-based assessments, a clinical response of progressive metabolic disease (PMD), no metabolic response (NMR), partial metabolic response (PMR), or complete metabolic response (CMR) will be determined. PMD/PD includes radiological evidence of progression per Lugano Classification Revised Staging System for malignant lymphoma⁶⁹. The PET scan metabolic uptake will be graded using the Deauville 5-point scale, with a score of ≤ 3 considered to represent a CMR.

Deauville 5-point scale: 1 = no uptake above background; 2 = uptake \leq mediastinum; 3 = uptake $>$ mediastinum but \leq liver; 4 = uptake moderately $>$ liver; 5 = uptake markedly higher than liver and/or new lesions; X = new areas of uptake unlikely to be related to lymphoma.

CONFIDENTIAL

This document is confidential. Do not disclose or use except as authorized.

Table 5: CMR / CR

Response/Site	FDG PET-CT-Based (Complete Metabolic Response)	CT-Based (CR) ^a All of the following:
Lymph nodes and extralymphatic sites	Score 1, 2 or 3 with or without a residual mass on 5-Point-Scale. It is recognized that in Waldeyer's ring or extranodal sites with high physiologic uptake or with activation within spleen or marrow (eg, with chemotherapy or myeloid colony-stimulating factors), uptake may be greater than normal mediastinum and/or liver. In this circumstance, complete metabolic response may be inferred if uptake at sites of initial involvement is no greater than surrounding normal tissue even if the tissue has high physiologic uptake.	Target nodes/nodal masses must regress to ≤ 1.5 cm in LDi No extra lymphatic sites of disease
Non-measured lesion	Not applicable	Absent
Organ enlargement	Not applicable	Regress to normal
New lesions	None	None
Bone marrow ^b	No evidence of FDG-avid disease in marrow	Normal by morphology; if indeterminate, IHC negative

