^a CT-Based could also apply to MRI-based

^b Only if bone marrow involvement at diagnosis

Table 6: PMR / PR

Response/Site	FDG PET-CT-Based (Complete Metabolic Response)	CT-Based (CR) ^a All of the following:
Target nodes/nodal masses, extranodal lesions	Score 4 or 5 with reduced uptake compared with baseline and residual mass(es) of any size At interim, these findings suggest responding disease At end of treatment, these findings suggest residual disease	≥ 50% decrease in SPD of up to 6 target measurable nodes and extranodal sites When a lesion is too small to measure on CT, assign 5mm X 5mm as the default value; when no longer visible, 0 X 0mm; for a node > 5mm X 5mm, but smaller than normal, use actual measurement for calculation
Non-measured lesion	Not applicable	Absent/normal, regressed, but no increase
Organ enlargement	Not applicable	Spleen must have regressed by >50% in length beyond normal
New lesions	None	None
Bone marrow ^b	Residual uptake higher than uptake in normal marrow but reduced compared with baseline (diffuse uptake compatible with reactive changes from chemotherapy allowed). If there are persistent focal changes in the marrow in the context of a nodal response, consideration should be given to further evaluation with MRI or biopsy or an interval scan.	Not applicable

^a CT-Based could also apply to MRI-based

^b Only if bone marrow involvement at diagnosis

Table 7: NMR/ SD

Response/Site	FDG PET-CT-Based (Complete Metabolic Response)	CT-Based (CR) ^a All of the following:
Lymph nodes and extralymphatic sites	Score 4 or 5 with no significant change in FDG uptake from baseline at interim or end of treatment	< 50% decrease in SPD of up to 6 target measurable nodes and extranodal sites; no criteria for Progressive Disease met
Non-measured lesion	Not applicable	No increase consistent with Progression
Organ enlargement	Not applicable	No increase consistent with Progression
New lesions	None	None
Bone marrow ^b	No change from baseline	Not applicable

^a CT-Based could also apply to MRI-based

^b Only if bone marrow involvement at diagnosis

Table 8: PMD / PD

Response/Site	FDG PET-CT-Based (Complete Metabolic Response)	CT-Based (CR) ^a All of the following:

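### Section 13.3 defines a responder in both strata by the LCH criteria of 9.1, and nothing says which Stratum 2 categories in 9.2 count as a response

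*Combined protocol and SAP*

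**What the plan says.** Section 5 announces two strata and gives the reason: "Patients will be stratified into two groups for response analysis purposes". Section 9 follows this with two sets of criteria.

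- **Stratum 1 (sections 9 and 9.1).** These criteria were "designed by the Histiocyte Society to be applied in therapeutic studies of LCH". Table 3 defines regressive disease as "Regression of signs/symptoms, and no new lesions", with no size threshold. Table 4 places complete resolution and regression together under *Better*.
- **Stratum 2 (section 9.2).** This is a Lugano/Deauville system. For PET, progressive disease, no metabolic response, "partial metabolic response (PMR), or complete metabolic response (CMR) will be determined". The CT column, which may also be used for MRI, has CR, PR, SD and PD.

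Section 13.3 opens with "The primary endpoint within each stratum will be the proportion of responders" and then defines a responder once, as a participant with complete resolution or regression, "i.e., their disease gets 'Better' per section 9.1". Section 9.2 is not cited there. Section 13.4 requires a response category under section 9 for each participant. Section 13.6 calculates the proportion of responders, with 95% confidence intervals, in Stratum 2 and in its subgroups.

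**The concern.** The responder rule for Stratum 2 points to criteria written for the other stratum. Taken literally, 13.3 tells the analyst to judge Stratum 2 patients by the LCH scheme. Taken together, 13.4 and 9.2 give those patients a Lugano category, but no section says which categories belong in the numerator.

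Objective 1.4.c asks for a description of responses in the LCH-related disorders, and 13.1 intends the subgroup rates to generate hypotheses for a later protocol. If the numerator is open, the reported rate depends on who analyses the data, and the choice could be made after the results are seen.

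**Working it through.** **1. The only figures in the plan built on responder status.** The plan gives no precision or power figure for Stratum 2 response. Rule A in 13.5 (Stratum 1; continue with at least 8 of 13, succeed with at least 14 of 20) was recomputed as

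P(success | p) = Σ over x = 8 to 13 of Bin(x; 13, p) × P[Bin(7, p) ≥ 14 − x].

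- p = 0.53: 0.0932 (plan: 0.093).
- p = 0.80: 0.908 (plan: 91%).

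Both agree to the stated rounding. Rule A uses Stratum 1 only, where the reference to 9.1 is correct, so this point does not touch it.

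**2. The two systems side by side, CT or MRI, no new lesions and no progression.**

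| Change | 9.1 (Tables 3 and 4) | 9.2 (Tables 6 and 7) |
|---|---|---|
| SPD falls by 50% or more | *Better* | PR, if the other PR rows are met |
| SPD falls by less than 50%, judged a regression | *Better* | SD |
| No change | Intermediate | SD |

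The middle row is the conflict. Its width is not fixed. Table 4 calls the intermediate category unchanged, and no section says how small a decrease still counts as regression. On PET, PMR also has no numeric threshold, so the conflict is shown for CT and MRI only.

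**3. A hypothetical case.** One lesion goes from 2.0 × 2.0 cm to 1.7 × 1.7 cm, with no new lesions.

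- Product of diameters: 4.00 to 2.89; fall = 1 − 2.89/4.00 = 27.75%.
- Under Table 7 this is SD. If the assessor calls it regression, it is *Better* under 9.1 and a responder under 13.3.
- With equal proportional shrinkage d in both diameters, the fall is 1 − (1 − d)². It stays below 50% for d up to 1 − √0.5, about 29% per diameter.

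**4. Whether another section closes the gap.** Section 13.4 asks for a category but does not sort categories into responders and non-responders. Section 13.6 uses the word responders without redefining it. Section 9.3 adds only a duration of 8 weeks.

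**5. Effect on the estimate.** One reclassified participant moves the rate by 1/N:

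- N = 20 (maximum in 13.2): 1/20 = 5 points.
- N = 10 (assumed, since 13.2 expects fewer than 20): 1/10 = 10 points.
- Average subgroup at maximum accrual: 20 patients over the five disorders named in 1.1 = 4 patients; 1/4 = 25 points.

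Illustration with an assumed 50% rate under 9.2, one participant reclassified, and exact (Clopper-Pearson) 95% intervals. The plan names no interval method.

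| N | Under 9.2 | One reclassified |
|---|---|---|
| 20 | 10/20 = 50% (27.2 to 72.8) | 11/20 = 55% (31.5 to 76.9) |
| 10 | 5/10 = 50% (18.7 to 81.3) | 6/10 = 60% (26.2 to 87.8) |
| 4 | 2/4 = 50% (6.8 to 93.2) | 3/4 = 75% (19.4 to 99.4) |

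**The case against.** The strongest reply is that the intended mapping can be recovered. Section 13.3 describes a responder in words before it cites 9.1, and the category names in 9.2 (complete response, partial response) suggest which ones count. The PET column of Table 6 remarks that PMR findings at an interim scan point to responding disease, and End of Cycle 2 is an interim time point in a course of up to six cycles. On this view the fault is a missing cross-reference.

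That is a plausible guess at intent, and the fix adopts it. It does not remove the fault. The Table 6 remark is descriptive, covers PET only, and says nothing about CT or MRI. The one explicit rule, in 13.3, sends the reader to 9.1, so a careful literal reader reaches a different numerator.

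Three further points stand as limits on size:

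- The conflict needs an assessor to call an SPD fall below 50% a regression, which may never happen.
- Stratum 2 response is exploratory, with no test, power claim or response stopping rule.
- At N = 4 the interval runs from 6.8 to 93.2, so a subgroup rate says little under either definition.

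Two related gaps are separate from this point: which result governs when PET and CT disagree, and how the 8-week duration in 9.3 fits with the End of Cycle 2 cutoff.

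**Conclusion.** The point holds. The plan states one responder rule for both strata, that rule refers to the Stratum 1 criteria, and no section maps the Stratum 2 categories to responder status. On CT or MRI, a Stratum 2 participant recorded as SD under 9.2 can be a responder under 13.3.

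The consequence is confined to the Stratum 2 response rates under objective 1.4.c. At N = 20 a one-participant shift is small against an interval 45.6 points wide (72.8 − 27.2). In subgroups the shift in points is larger, but the intervals there are very wide in any case. The 50% starting rate, N = 10 and the even split over five diseases are assumptions, and the number of participants affected cannot be derived from the documents. This should be corrected before the Stratum 2 data are analysed; it does not threaten the primary objective or Rule A.

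**What to change.** In 13.3, limit the reference to 9.1 to Stratum 1 and add a sentence for Stratum 2, for example: *In Stratum 2, a responder is an eligible, evaluable participant whose best overall response under section 9.2, up to and including the End of Cycle 2 assessment, is CMR/CR or PMR/PR.*

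The cost is one sentence. No new data or visits are needed, because 13.4 already requires a section 9 category for every participant. The downside is that the reported Stratum 2 rate may be lower than under 9.1. The same edit would be a convenient place to say which category governs when PET and CT differ.
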